2.3 Exploratory

EO 1: To compare the proportions of participants with asthma exacerbations during the 14 and 42 days after receipt of LAIV4 or IIV4, by asthma severity group (Appendix 1).

EO 2: To compare the proportion of participants with asthma symptoms and unscheduled albuterol use during the 14 days after receipt of LAIV4 or IIV4, by asthma severity group.

EO 3: To compare the proportion of participants who experience a clinically significant decrease in PEFR from baseline during the 14 days after receipt of LAIV4 or IIV4, by asthma severity group.

EO 4: To describe and compare changes in Peak Expiratory Flow Rate (PEFR) from baseline (pre-vaccination) PEFR after vaccination over time during the 14 days after receipt of LAIV4 or IIV4, by asthma severity group.

EO 5: To compare change in Childhood Asthma Control Test (c-ACT) score (participants aged 5-11 years) or Asthma Control Test (ACT) score (participants aged 12-17 years) from baseline through 42 days after LAIV4 or IIV4, by asthma severity group

EO 6: To compare asthma symptom days using Preventative Omalizumab or Step-up Therapy for Severe Fall Exacerbations (PROSE) from baseline during the 14 days after vaccination by asthma severity group.

EO 7: To compare rates of medical utilization for asthma-related symptoms during the 14 and 42 days after LAIV4 or IIV4, by asthma severity group.

EO 8: To describe and compare systemic reactogenicity events during the 14 days after receipt of LAIV4 or IIV4, by asthma severity group.

EO 9: To describe and compare serious adverse events after LAIV4 vs. IIV4 during the 42 days after vaccination and assess relatedness to vaccine.

EO 10: To describe and compare asthma symptoms and control among participants with and without a history of allergic rhinitis or hay fever, used as a proxy for allergic versus non-allergic asthma.

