4.2 Sample Size and Power

This study aims to enroll approximately 300 participants (approximately 100 from Vanderbilt, approximately 110 from Cincinnati, and approximately 90 from Duke). We assume that the proportion of participants with asthma exacerbation(s) in 42 days after vaccination is 12% after LAIV4 and IIV4 [1]. We also assume that ~10% of the children may drop out, yielding a total sample of at least 270 (135 LAIV4 and 135 IIV4).

Our research hypothesis is that the proportion of participants with asthma exacerbation(s) in the LAIV4 (experimental group) will not be higher than in the IIV4 group (control group). The power estimate is shown below, given delta of 10% and one-sided alpha is set at 5% level.

Proportion of participants with asthma exacerbation(s) in control IIV4 group (pc)	Proportion of participants asthma exacerbation(s) in LAIV4 experimental group (pe)	Estimated power to reject H0: pe – pc >= 10%
---	--	---

12%	12%	81.1%
-----	-----	-------

The null hypothesis is that the proportion of participants with asthma exacerbation(s) in the LAIV4 group will be inferior (higher) than the proportion in the IIV4 group. The null hypothesis will be rejected (and delta margin noninferiority claimed) when the upper bound of the 95% one-sided confidence interval for the pe minus pc is less than 10%. IBM SPSS SamplePower software version 3.0.1 was used for the power calculation which was not adjusted for stratifying by site.

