4.3 Randomization

Participants will be randomized (1:1) to receive either a single intranasal dose of licensed quadrivalent LAIV4 or an intramuscular injection of quadrivalent inactivated influenza vaccine (IIV4), stratifying by asthma severity (mild vs. moderate/severe) in both influenza seasons and age group (5-11 and 12-17 years old) in the second influenza season (2019-20). The permuted block randomizations will be done separately for each site (i.e., Vanderbilt University Medical Center, Duke University Medical Center and Cincinnati Children's Hospital Medical Center), with varying block size of either 4 or 6. Each site may have more than one clinic to recruit participants, and proportions of participants with mild or moderate/severe asthma can vary by clinics. Randomization will be accomplished using the REDCap System, hosted at Vanderbilt. Since this is a web-based system, it is easily accessible to the other collaborating sites as well. This study will be open label and study staff and subjects will not be blinded to treatment arm assignments.

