8 ANALYSIS OF STUDY OBJECTIVES

Descriptive analyses will be summarized for continuous variables with mean, standard deviation, median, and interquartile range. Categorical variables will be summarized with frequencies and percentages. Explanatory figures will be generated to evaluate the data distribution. Comparisons of demographic characteristics between LAIV4 and IIV4 groups will be conducted using Pearson Chi-square and Wilcoxon tests appropriately.

All analyses will be performed using R 3.6.2 (r-project.org), SAS version 9.4, or STATA version 16, or updated software from these programs.

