For each reactogenicity reaction, summary statistics will be performed such as frequencies and percentages for categorical variables and mean/standard deviation or median/interquartile range for continuous variables. Results will be presented as none, mild, moderate and/or severe reactions. There will be statistical comparisons among moderate/severe reactogenicity reactions by treatment groups and asthma severity groups (Mild vs. Moderate-Severe) using Mantel-Haenszel tests.

- i) The ninth exploratory objective (EO 9) is to describe and compare serious adverse events during the 42 days after LAIV4 or IIV4 and assess relatedness to vaccine

For each serious adverse event and assessing relatedness, summary statistics will be performed such as frequencies and percentages for categorical variables and mean/standard deviation or median/interquartile range for continuous variables. The Mantel-Haenszel test will be used for comparisons of proportions of having at least one SAE by treatment groups and asthma severity levels. Listing of the serious adverse events by study LAIV4 or IIV4 groups will also be presented.

- j) The tenth exploratory objective (EO 10) is to describe and compare asthma symptoms and asthma control (PROSE, and c-ACT/ACT scores) among participants with and without a history of allergic rhinitis or hay fever, as a proxy for allergic versus non-allergic asthma.

For each asthma symptom and control, summary statistics will be performed such as frequencies and percentages for categorical variables and mean/standard deviation or median/interquartile range for continuous variables. The Mantel-Haenszel test will be used for comparisons of proportions of having at least one symptom by treatment groups and allergic asthma status (history of allergy rhinitis or hay fever vs. no history of these conditions).

No adjustments will be made to the alpha level (two-sided alpha=0.05) for these exploratory objective analyses.

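### The only planned inferential comparison of serious adverse events between vaccines (EO 9) is a Mantel-Haenszel test; it should lead with a confidence interval that is defined at zero counts

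*SAP*

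**What the plan says.** The objective in SAP section 2.3 is comparative: "EO 9: To describe and compare serious adverse events after LAIV4 vs. IIV4 during the 42 days after vaccination and assess relatedness to vaccine". Section 8.3, item i, gives the method. It plans frequencies and percentages, an assessment of relatedness, and one test: "The Mantel-Haenszel test will be used for comparisons of proportions of having at least one SAE by treatment groups and asthma severity levels". It adds: "Listing of the serious adverse events by study LAIV4 or IIV4 groups will also be presented". The closing line of section 8.3 sets the level: "No adjustments will be made to the alpha level (two-sided alpha=0.05) for these exploratory objective analyses".

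Section 8 leaves the software open: "All analyses will be performed using R 3.6.2 (r-project.org), SAS version 9.4, or STATA version 16, or updated software from these programs". Neither section says whether the test is asymptotic or exact, whether a continuity correction applies, or what is reported if there are no SAEs. Protocol section 8.2 leaves the methods for exploratory objectives to the SAP, so the protocol does not fill the gap.

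Other analyses get more. SAP section 8.1 plans a difference and interval for the primary endpoint. Section 8.2 plans differences with 95% intervals for SO 2 and SO 3. Section 8.3 plans 95% intervals for the maximal peak-flow change under EO 4. SAP section 6 assigns analysis populations only to the primary and secondary objectives, so the EO 9 denominator is also unstated.

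**The concern.** An SAE comparison in a trial of this size will probably rest on few events. A test alone then says little. With no events it does not exist. With a few events split one-sidedly, reasonable versions of the same named test can fall on either side of 0.05. With a balanced split it returns a large p-value that does not say how much harm remains possible.

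Protocol section 5.1.2 allows that children with asthma might have more exacerbations after LAIV4 than after the inactivated vaccine, and a hospitalization counts as an SAE (protocol sections 4.10 and 6). A reader of a vaccine-safety trial therefore wants to know how large an SAE excess the data rule out. EO 9 as written does not plan that statement.

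**Working it through.** **Inputs from the documents.** Enrolment: "This study aims to enroll approximately 300 participants (approximately 100 from Vanderbilt, approximately 110 from Cincinnati, and approximately 90 from Duke"). Evaluable number: "We also assume that ~10% of the children may drop out, yielding a total sample of at least 270 (135 LAIV4 and 135 IIV4"). Allocation: "Participants will be randomized (1:1) to receive either a single intranasal dose of licensed quadrivalent LAIV4" or IIV4. EO 9 is two-sided at 0.05.

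**Assumed, because the documents give no figure.** SAE risk over 42 days of 0.5% to 3%; two severity strata of nearly equal size, 68 and 67 children per arm.

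**The plan's own figure.** The only stated power is for the primary test. The standard error is √(2 × 0.12 × 0.88 / 135) = 0.0396. Power is Φ(0.10 / 0.0396 − 1.645) = Φ(0.88) = 81.1%, as stated. No rate, count or power is stated for SAEs.

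**Expected SAE counts.** 300 × 0.005 = 1.5 and 300 × 0.03 = 9. The chance of none in 300 is (1 − risk)^300: 22% at 0.5%, 4.9% at 1%, 0.2% at 2% and 0.01% at 3%.

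**The test.** Let stratum k have n children per arm and m events in total, a of them after LAIV4. Then X² = (|Σ(a − m/2)| − c)² / ΣV, with V = m(2n − m) / [4(2n − 1)]. Here c is 0 without the continuity correction and 0.5 with it. With no events ΣV = 0, so X² is 0/0.

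For 4 v 0 with two events in each stratum:
- ΣV = 2 × 134 / (4 × 135) + 2 × 132 / (4 × 133) = 0.4963 + 0.4962 = 0.9925.
- Uncorrected: 2² / 0.9925 = 4.03, p = 0.045.
- Corrected: 1.5² / 0.9925 = 2.27, p = 0.13.
- Exact conditional test stratified by severity: p = 0.12.

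Other splits:

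| Split | Uncorrected p | Corrected p | Crosses 0.05? |
|---|---|---|---|
| 4 v 0 | 0.045 | 0.13 | yes |
| 5 v 0 | 0.024 | 0.072 | yes |
| 7 v 1 | 0.032 | 0.074 | yes |
| 6 v 0 | 0.014 | 0.040 | no |
| 3 v 1 | 0.32 | 0.62 | no |
| 2 v 2 | 1.00 | not significant | no |

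With 150 per arm these values hardly move.

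**How often the versions disagree.** I enumerated all binomial counts at 135 per arm. With equal risks of 0.5%, 1%, 2% and 3%, the corrected and uncorrected tests differ at 0.05 in 0.5%, 2.3%, 3.6% and 2.7% of trials. At 1% v 3% they differ in 12%. With equal risks the uncorrected test rejects 2.5% of the time at 1% and 4.5% at 2%, so its long-run size stays below 5%.

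**What an interval would add.** For 0 v 0, the Miettinen-Nurminen limit d solves 135 × (269/270) × d / (1 − d) = 3.84, so d / (1 − d) = 0.0286 and d = 2.8 points. By iteration, at 135 per arm (LAIV4 minus IIV4, percentage points):
- 0 v 0: −2.8 to +2.8.
- 2 v 1: −2.7 to +4.6.
- 4 v 0: +0.15 to +7.4.

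The exact (Clopper-Pearson) upper limit for one group with 0 of 135 is 1 − 0.025^(1/135) = 2.7%.

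**The case against.** The case for leaving EO 9 alone is substantial, and much of it stands.

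- EO 9 is one of ten exploratory objectives, unadjusted and with no decision attached.
- It is not only a p-value. Percentages and a listing by vaccine are planned, so a reader could work out an interval. Asthma hospitalizations also count towards the primary endpoint, which has a difference and an interval.
- A reader might infer that the test is unreliable whenever there are four SAEs. It is not: four events change the verdict only when split 4 v 0.
- A reader might infer inflated type I error. The enumeration does not show it.
- A reader might blame the method for missing real harm. At 1% v 3% the uncorrected test reaches 0.05 only about 20% of the time, but that follows from the sample size. An exact test does worse.
- A reader might take it as given that SAEs will be few, that the test is the large-sample version, or that the listed packages differ in their defaults. The documents state none of these. They give no SAE rate, neither name nor exclude an exact version, and only list the packages.
- With no SAEs, nobody would try to interpret a test.

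What remains is narrower. An interval worked out by a reader, or added later, has a method chosen after the data are seen. With no SAEs, an interval still says something (here ±2.8 points) and the planned test says nothing. The plan gives SO 2, SO 3 and part of EO 4 an interval but not the comparison of serious harm.

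A careless remedy would recreate the ambiguity. At 4 v 0 the score interval excludes zero while the exact p is 0.12, and a Newcombe interval (−0.34 to +7.37 points) includes zero. One method has to be named and given precedence.

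**Conclusion.** The point holds as a minor one. EO 9 sets out to compare SAEs between vaccines, but its only inferential output is a test with no estimate or interval. That test is undefined with no events and can turn on an unstated continuity correction at some lopsided splits. Disagreement is uncommon: about 0.5% to 3.6% of trials with no vaccine effect, and about 12% at 1% v 3%. The more general gap is that no planned output says what SAE excess after LAIV4 the data exclude.

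The sizes rest on the assumed SAE risk of 0.5% to 3%, about 135 children per arm and near-equal severity strata. The absence of an interval and the undefined result at zero do not depend on those assumptions. No primary or secondary conclusion is affected.

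**What to change.** In SAP section 8.3, item i:

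1. Make the main EO 9 comparison the LAIV4 minus IIV4 difference in the proportion of children with at least one SAE. Give a 95% interval by one named method that is defined at zero counts, for example Miettinen-Nurminen.
2. State the population as all vaccinated children.
3. Report the proportion in each vaccine group with an exact (Clopper-Pearson) 95% interval.
4. Keep the SAE listing by vaccine group.
5. If a p-value is kept, use the exact conditional test stratified by severity and label it supportive. State in advance that the interval leads, because the two can disagree (as at 4 v 0).

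The cost is a few lines of SAP text and code, with no new data or sample size. The drawback is that the exact p-value is conservative. At an assumed 1% v 4% with 135 per arm it reaches 0.05 about 19% of the time, against 34% for the uncorrected test. That is a further reason for the interval to lead.

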9 PROTOCOL DEVIATIONS

See Appendix 2

10 SENSITIVITY ANALYSES

If applicable, sensitivity analyses on primary and secondary objectives will be done on datasets defined by treatment group. If applicable, sensitivity analyses on primary and secondary objectives will be done on datasets defined by treatment group. For example, if a participant was assigned to LAIV4 and inadvertently received IIV4 that participant would be reassigned to the IIV4 treatment group in the sensitivity analyses.

11 REFERENCES

1. Fleming, D.M., et al., *Comparison of the efficacy and safety of live attenuated cold-adapted influenza vaccine, trivalent, with trivalent inactivated influenza virus vaccine in children and adolescents with asthma*. *Pediatr Infect Dis J*, 2006. **25**(10): p. 860-9.

Appendix 1

Table 1: Asthma severity categories and prescription long-acting controller medications* for children with persistent asthma, aged 5-17 years

Classification of Asthma Severity		
Treatment of Persistent Asthma		
Mild Persistent	Moderate Persistent	Severe Persistent
Low-dose ICS OR Montelukast OR Cromolyn sodium	Low-dose ICS + Montelukast OR Low-dose ICS + LABA OR Medium-dose ICS	Medium-dose ICS + Montelukast or LABA OR Any High-dose ICS OR Omalizumab/Xolair OR Mepolizumab/Nucala OR Chronic systemic steroids

Abbreviations: LABA: long-acting beta-agonist; ICS: inhaled corticosteroids

**Controller medications include inhaled corticosteroids, oral corticosteroids, leukotriene receptor antagonists, long-acting beta agonists, and biologics.*

